5.4.4.3.3. Post-treatment-emergent adverse events

The following summaries are presented:

- Post-treatment-emergent AEs by SOC and PT (frequency; AP3 only, completed/discontinued subjects only).
- Post-treatment-emergent AEs by SOC and PT (frequency; AP3 only, completed/discontinued subjects only) by Treated (DMTs, including ponesimod), Not treated and Total.

A listing of all post-treatment AEs is provided based on the PAS.

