- Visit FU1 (Follow-up visit 1): 8 days after the last study drug intake.
- Visit FU2 (Follow-up visit 2): 30 days after the last study drug intake.
- Visit FU3 (Follow-up visit 3):
- 90 days after the last study drug intake.

Patients who discontinue study drug prematurely must have the corresponding Safety Follow-up visits after their last study drug intake.

These visits and assessments will also be conducted for patients who have switched to commercially available ponesimod.

End-of-study (EOS2/EOS3)

- End-of-study (EOS) visit 2 (EOS2) for an individual patient is reached 30 days after the last dose of study drug in TP1.
- Patients not enrolling into TP2 have to perform EOS2.
- EOS3 for an individual patient is reached 90 days after the last dose of study drug for patients that have enrolled into TP2 and TP3, if applicable.
- Patients not enrolling into TP3 have to perform EOS3.
- The maximum duration of this extension study for an individual patient is up to 649 weeks (636 weeks of treatment extension, and 90 days of follow-up).

Patients will follow the standard of care after completing the study.

EudraCT 2009-011470-15

EDMS-ERI-206617631

Ponesimod / ACT-128800 / JNJ-67896153 Multiple Sclerosis Protocol AC-058B202 Version 12 15 March 2022, page 57/179

Confidential

Figure 1: Study design

AC-058B201 (Core Study)		AC-058B202 (Extension Study)	
24 weeks	Up to 96 weeks	Up to 540 weeks	Up to 90 days
10 mg ponesimod ·	► 10 mg ponesimod	→ 10 mg ponesimod → 20 mg ponesimod	
20 mg ponesimod	► 20 mg ponesimod	→ 20 mg ponesimod → 20 mg ponesimod	
40 mg ponesimod ·	► 40 mg ponesimod	1:1 \checkmark 10 mg ponesimod \rightarrow 20 mg ponesimod 20 mg ponesimod \rightarrow 20 mg ponesimod	
	10 mg ponesimod	→ 10 mg ponesimod → 20 mg ponesimod	
Placebo -	→1:1:1 → 20 mg ponesimod	$\longrightarrow 20 \text{ mg ponesimod} \qquad \longrightarrow 20 \text{ mg ponesimod}$ $ 10 \text{ mg ponesimod} \qquad \longrightarrow 20 \text{ mg ponesimod}$	
	40 mg ponesimod	1:1 < 20 mg ponesimod → 20 mg ponesimod	
Transition	Ex	atension Treatment Periods	
Informed Consent	Period 1 Randomization	Period 2 Period 3	Follow-up*
Up to Visit 11 3 days Veek 24	Period 1 Visits: E1 until E13 Period 1 Week: 1 until 96	(EOT2) Period 2 / 3 Visits: P1 until EOT3 Period 2 / 3 Week: 1 until 540	

*Safety follow-up visits:

After treatment period 1: at 8 and 30 days after last dose of study drug

After treatment period 2 and treatment period 3: at 8, 30 and 90 days after last dose of study drug

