4 SAFETY DEFINITIONS AND REPORTING REQUIREMENTS

4.1 Summary table

Periods	Treatment (including transition and study drug interruption)	Follow-up ²	After Follow-up
Time frame	During study drug administration until 15 days after study drug discontinuation and during study drug interruption	Treatment period 1: From 16 until 30 days after study drug discontinuation Treatment periods 2 and 3: From 16 until 90 days after study drug discontinuation	Treatment period 1: After 30 days Treatment periods 2 and 3: After 90 days
AE/SAE reporting on eCRF AE form	All AEs/SAEs	All AEs/SAEs	None
SAE reporting on SAE form	All SAEs	All SAEs	If felt appropriate by investigator
Reconciliation ¹	Yes	Yes	Not applicable

1. Reconciliation between clinical and drug safety databases.

2. AEs/SAEs occurring between treatment periods 1, 2 and 3 must be reported in the AE eCRF form.

AE adverse event; eCRF electronic case report form; SAE serious adverse event.

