5.1.6. Post-treatment-emergent definition

The post-treatment-emergent period is defined as follows:

The start date of the period is the date of last administration of ponesimod as study drug plus 16 days (inclusive). See Section 5.1.4 for the definition of treatment-emergent, which is defined as the time from first administration of ponesimod up to 15 days (inclusive) after last administration of ponesimod as study drug.

The end date of the period is last study date [see Section 5.1.1].

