5.4.3.2. Post-treatment-emergent adverse events

Post-treatment-emergent adverse events are defined as those AEs occurring from 16 days after last administration of ponesimod until last study date, i.e., AEs occurring during the post-treatment-emergent period (Section 5.1.6)

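### The post-treatment AE tables give crude percentages pooled over follow-up windows of about 15 and 75 days, so the Treated and Not treated columns are not comparable if their mix of leavers differs

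*SAP*

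**What the plan says.** SAP 5.4.3.2 defines the events: "Post-treatment-emergent adverse events are defined as those AEs occurring from 16 days after last administration of ponesimod until last study date". The last study date depends on when the patient stopped. Protocol 3.1.1 states that "End-of-study (EOS) visit 2 (EOS2) for an individual patient is reached 30 days after the last dose of study drug in TP1", and that "EOS3 for an individual patient is reached 90 days after the last dose of study drug for patients that have enrolled into TP2"; the same 90 days apply to patients who go on to TP3. The safety summary table in Protocol 4.1 sets the matching AE collection windows: "Treatment period 1: From 16 until 30 days after study drug discontinuation Treatment periods 2 and 3: From 16 until 90 days".

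SAP 5.4.4.3.3 lists two summaries of these events, both by frequency. One is not split by later therapy. The other is "Post-treatment-emergent AEs by SOC and PT (frequency; AP3 only, completed/discontinued subjects only) by Treated (DMTs, including ponesimod), Not treated and Total". Under SAP 5.4.4.2 and 5.4.4.3, frequency means the number and percentage of subjects with an event, each subject counted once.

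SAP 5.4.4.2 also defines AEs per 100 subject-years, but gives an observation time only for treatment-emergent AEs. The rate tables for all AEs are listed in 5.4.4.3.2, which covers treatment-emergent events; 5.4.4.3.3 lists none.

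The relapse analysis of the same period is handled differently. SAP 5.3.1.4 derives each subject's length of post-treatment observation in years, and 5.3.2.2 divides relapses by total time within the DMT / no DMT split.

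**The concern.** A percentage with any event rises with the time watched. These tables put patients watched for about two weeks and patients watched for about eleven weeks into one denominator, then set patients on a later disease-modifying therapy (DMT) beside patients on none. If TP1 leavers make up a different share of the two columns, the columns differ even when the AE rate is the same in everyone.

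Two features of the plan could create such a difference:

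- Ponesimod counts as a DMT (SAP 5.5.6 and Table 11), and the commercial-availability completion category is derived for TP3 only (SAP 5.2.1.5). Patients who switch to commercial drug are scheduled for the 90-day follow-up.
- Concomitant medications are recorded only to EOS2 or EOS3 (Protocol 3.11.5.3). A TP1 leaver has 30 days in which a DMT can appear in the data, and a TP2/TP3 leaver has 90.

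Both make longer windows in Treated plausible. At stake is the reading of a safety table: events after stopping could seem linked to later therapy when the difference comes from follow-up time.

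**Working it through.** **Window lengths.** The start is last dose + 16 days (SAP 5.1.6). The end is day 30 for TP1 leavers and day 90 for TP2/TP3 leavers (Protocol 3.1.1 and 4.1). The documents give the end points; the lengths follow.

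- TP1: 30 - 16 + 1 = 15 days (10 to 20 with the ±5-day visit window).
- TP2/TP3: 90 - 16 + 1 = 75 days (68 to 82 with the ±7-day visit window).
- Ratio: 75/15 = 5.0 (from 68/20 = 3.4 to 82/10 = 8.2).

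As a check on the 90-day end point, 636 + 90/7 = 648.9 weeks, which agrees with the 649-week maximum in Protocol 3.1.1.

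**Effect of window length alone.** Assume one constant AE rate r in everyone, so P(any AE) = 1 - exp(-r × days/365.25). The documents give no post-treatment AE rate; r is an assumption.

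| r per patient-year | 15 days | 75 days | Ratio |
|---|---|---|---|
| 1 | 4.0% | 18.6% | 4.6 |
| 2 | 7.9% | 33.7% | 4.3 |
| 3 | 11.6% | 46.0% | 4.0 |

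**Effect on the split.** A column's percentage is s × P(15 days) + (1 - s) × P(75 days), where s is the share of 15-day leavers in that column. The documents give no value of s for either column, so every case below is an assumed scenario with no true difference in AE rate.

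- *Upper scenario, r = 2.* No 15-day leavers in Treated: 33.7%. Not treated with s = 30%: 0.3 × 7.9 + 0.7 × 33.7 = 25.9% (unrounded inputs). With s = 50%: 20.8%. The gap is about 8 to 13 points.
- *Same, but 20% 15-day leavers in Treated.* Treated becomes 0.2 × 7.9 + 0.8 × 33.7 = 28.5%, and the gap falls to about 3 to 8 points.
- *Recording window only.* Every leaver starts a DMT at the same hazard, but starts are seen to day 30 or day 90. With 30% TP1 leavers and 40% on a DMT by day 30, uptake by day 90 is 1 - 0.6³ = 78%. TP1 leavers are then 18% of Treated and 54% of Not treated. At r = 1 the columns read 16.0% and 10.7%, a ratio of 1.50. Over TP1 shares of 20-40%, day-30 uptake of 20-60% and r of 1-2, the ratio runs from 1.18 to 2.08.
- *Equal recorded uptake in TP1 and TP2/TP3 leavers.* The ratio is 1.0.
- *Higher uptake in TP1 leavers (50% against 30%).* The ratio is 0.79 to 0.88, so the bias reverses.

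On a person-time scale with one common rate, the ratio is 1.0 in every scenario.

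**Limits.** The documents do not state the follow-up length of patients who left after the core study alone, so the 15/75 contrast is documented for extension leavers only. Death and loss to follow-up shorten some windows. A planned-pregnancy interruption that is never restarted could lengthen one.

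**The case against.** The strongest reply is that no passage gives DMT uptake by treatment period. Treated covers every agent in Table 11, including interferon beta, glatiramer and natalizumab, and TP1 leavers could start any of these. Protocol 3.12.5.1 tells investigators to remind patients of approved alternatives after a confirmed relapse. This stands: the direction is plausible and not established, and the size cannot be computed from the documents.

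The tables are also descriptive. All objectives are exploratory (SAP 2), p-values were removed (SAP 6.2.3), no between-column hypothesis is stated, and a full listing accompanies the tables. This stands too, and limits the harm to misreading. A listing does not, however, make the two percentages comparable.

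A third reply is that SAP 5.4.4.2 already says AEs are summarized both by frequency and per 100 subject-years. This does not answer the point, because the section defines no observation time for the post-treatment period and 5.4.4.3.3 names no rate table.

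A reader might infer more than the documents support: that the short windows fall mainly in Not treated, that AEs will look more frequent in Treated, or that the gap will be 8-13 points. The first two need uptake figures that are not given. The third also assumes that no early leaver is in Treated, whereas SAP 5.5.6 places any leaver with a qualifying DMT record there, whichever period they left.

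**Conclusion.** The point holds in a limited form. The documents establish that the post-treatment AE percentages pool windows of about 15 and 75 days with no adjustment for time, while the relapse rate for the same period is divided by observation time. At a common rate of 1-3 AEs per patient-year (assumed, constant over time), window length alone moves the chance of any AE from 4.0%-11.6% to 18.6%-46.0%. The overall table therefore mixes two quantities, and the split table is not interpretable across columns whenever the TP1 share differs between them.

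Whether it does differ, and in which direction, is not documented. The TP3-only commercial category and the 30-day against 90-day medication recording favour longer windows in Treated. Zero bias and reversal both remain possible. No formal test is affected.

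**What to change.** In SAP 5.4.4.3.3:

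1. Add AEs per 100 subject-years of post-treatment observation to both tables, using the length of observation already derived in SAP 5.3.1.4 as the denominator.
2. Show the frequencies separately for TP1 leavers and TP2/TP3 leavers or, at the least, report total follow-up time under each column.
3. State how core-only leavers are handled and what their follow-up length is.

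Restricting the Treated / Not treated split to TP2/TP3 leavers is an option, not a necessity.

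The cost is some SAP wording, reuse of an existing variable and extra table columns. The downside is sparse cells by system organ class and preferred term. A rate also does not correct for a DMT started after the AE: SAP 5.5.6 classifies on whether a DMT record exists, so a patient can count as Treated for an event that came first. A footnote should say so.

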5.4.4.3.4. Adverse events ongoing from the core study

A listing of all AEs ongoing from the core study is provided based on the PAS.

This listing was presented in the Interim Analysis CSR and is not planned to be presented in the Final CSR.

5.4.4.4. Deaths, other serious adverse events

5.4.4.4.1. Death

The number and percentage of subjects who died are summarized by treatment group, including the reported primary cause of death, for AP3 on the PAS.

All deaths during AP3 are listed on the PAS.

5.4.4.4.2. Serious adverse events

The following summaries are presented:

- Treatment-emergent SAEs by SOC and PT (frequency);
- Treatment-emergent SAEs with onset on Day 1 of first ponesimod administration, by SOC and PT (frequency) single table with a column for ponesimod 10 mg only;
- All SAEs by SOC and PT (frequency);
- Treatment-emergent SAEs by SOC and PT (AEs per 100 subject-years).

Separate listings including all SAEs are provided for AP3 on the PAS.

Treatment emergent SAEs with onset of Day 1 of first ponesimod administration, by SOC and PT (frequency) was presented in the Interim Analysis CSR and is not planned to be presented in the Final CSR.

5.4.4.4.3. Treatment-emergent AEs leading to study treatment discontinuation

The following summaries are presented:

- TEAEs leading to study treatment discontinuation by SOC and PT (frequency);
- TEAEs with onset on Day 1 of first ponesimod administration leading to study treatment discontinuation, by SOC and PT (frequency) single table with a column for ponesimod 10 mg only.

A separate listing including all AEs leading to study treatment discontinuation is provided for AP3 on the PAS.

Treatment emergent SAEs with onset of Day 1 of first ponesimod administration leading to study treatment discontinuation, by SOC and PT (frequency) was presented in the Interim Analysis CSR and is not planned to be presented in the Final CSR.

5.4.4.4.4. Treatment-emergent AEs leading to temporary interruption of study treatment

A listing including all AEs leading to temporary interruption of study treatment is provided for AP3 on the PAS.

5.4.4.4.5. Adverse events of special interest

The following summaries are presented:

- Treatment-emergent AESIs by AESI category and PT (frequency);
- Treatment-emergent AESIs by AESI category and PT (AEs per 100 subject-years).

The following additional (frequency) summaries are presented for the AESI category "Effect on heart rate and rhythm AESI (including hypotension)", for AEs relative to first administration of ponesimod:

- AEs by Day and PT, for Days 1-21;
- AEs on Days 1-7 (overall) by PT;
- AEs on Days 8-14 (overall) by PT;
- AEs on Days 15-21 (overall) by PT.

For summaries by Day following first ponesimod administration, subjects are summarized as follows:

- For Days 1-7 all subjects are summarized under ponesimod 10 mg;
- For Days 8-14 subjects randomized to ponesimod 10 mg are summarized under ponesimod 10 mg, whilst subjects randomized to ponesimod 20 mg or ponesimod 40 mg are summarized under ponesimod 20 mg;
- For Day 15-21 all subjects are summarized under their randomized dose.

This reflects the up-titration scheme and the doses that subjects were receiving at the time.

Time to first treatment-emergent AESI is analyzed separately for each AESI category for AP3 on the PAS using the Kaplan-Meier method, as described in for time to first relapse in Section 6.12.2.

A separate listing including all AESIs is provided based for AP3 on the PAS.

The above summary tables for Days 1-7, 8-14 and 15-21 for the AESI category "Effect on heart rate and rhythm AESI (including hypotension)", for AEs relative to first administration of ponesimod were presented in the Interim Analysis CSR. As no new data are expected, this is not planned to be presented in the Final CSR.

Additionally, Time to first treatment-emergent AESI for each AESI category for AP3, using the Kaplan-Meier method, was presented in the Interim Analysis CSR and is not planned to be presented in the Final CSR.

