WHO	World Health Organization
WOCBP	Women of childbearing potential

EudraCT 2009-011470-15

EDMS-ERI-206617631

Ponesimod / ACT-128800/ JNJ-67896153 Multiple Sclerosis Protocol AC-058B202 Version 12 15 March 2022, page 14/179

Confidential

GLOBAL AMENDMENT 11

Amendment rationale

This amendment applies to global protocol AC-058B202 Version 11, dated 04 May 2021, and the following local protocol version:

• Final Version 10.GBR.C dated 27 October 2020

The resulting amended global protocol is Version 12, dated 15 March 2022. The relevant local protocol versions have also been updated (ie, for the UK).

The reasons for this substantial amendment are:

- To allow any EDSS/FS tool which is used at the site as a standard instrument.
- To introduce immunogenicity analysis into the statistical section.
- To remove the bronchodilator test at the scheduled PFT due to the prolonged length of the study.
- To narrow the scope of vaccine-specific antibody titers from pre- to post vaccination to patients having received non-live vaccination against influenza or COVID-19 while on study treatment.
- To update the requirement for OCT to be performed only in the case of visual symptoms suggestive of macular edema or active uveitis, as consistent with the observed dynamic of this event on Sphingosine-1-phosphate (S1P) treatment.
- To acknowledge the decommission of the Ophthalmology Safety Board (OSB). The number of cases of macular edema is expected to be low (most cases occur within the first 6 months of treatment) and no new patients will initiate treatment in the study. Therefore, an OSB review is no longer required and the OSB was disbanded for the ongoing long-term extension studies, its status has been clarified and where appropriate reference to the OSB has been removed.
- To confirm the disbandment of the IDMC.
- Clarifications and minor corrections have been added to the protocol.

Changes to the protocol

Two versions of the amended protocol will be prepared: 1) a clean version and 2) a Word comparison document, showing deletions and insertions in comparison to the previous protocol version.

Changes to the Patient information leaflet:

Where applicable, the same changes have also been made to the patient information leaflet.

Ponesimod / ACT-128800/ JNJ-67896153		EudraCT 2009-011470-15
Multiple Sclerosis		EDMS-ERI-206617631
Protocol AC-058B202	Confidential	
Version 12		
15 March 2022, page 15/179		

Amended protocol sections

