- In the AC-058B301/OPTIMUM study, the proportion of patients who experienced at least one TEAE was similar in both treatment arms (88.8% and 88.2% of patients in the ponesimod 20 mg and the teriflunomide 14 mg arms, respectively). The most common TEAEs in the ponesimod 20 mg arm were ALT increased (19.5%), nasopharyngitis (19.3%), headache (11.5%) and upper respiratory tract infections (10.6%). Initiation of ponesimod using the gradual uptitration regimen (starting with ponesimod 2 mg) was not associated with clinically significant bradyarrhythmia events; none of reported bradyarrhythmia events were serious or leading to discontinuation of treatment; no second- or higher degree AV blocks were reported.
- In the interim analysis of AC-058B202 (cut-off date of 31 March 2019), long-term treatment with ponesimod was not associated with new safety or tolerability concerns. Study AC-058B202 is ongoing. The results of the interim analysis support the long-term benefit/risk profile of the 20 mg dose as the most optimal dose of ponesimod. Ponesimod 20 mg was shown to be safe and well tolerated in adults with RRMS over long-term treatment of up to 9 years (median exposure to ponesimod in the 20 mg dose group of 8.02 years, corresponding to a total of 817 subject-years).

Ponesimod / ACT-128800 / JNJ-67896153 Multiple Sclerosis		EudraCT 2009-011470-15 EDMS-ERI-206617631
Protocol AC-058B202	Confidential	
Version 12		
15 March 2022, page 48/179		

Nonclinical safety testing of ponesimod indicates an embryotoxic and teratogenic potential. Pregnant or lactating women are excluded from clinical trials, and women of childbearing potential (WOCBP) must use two reliable methods of contraception and must not become pregnant while on study drug and for at least 30 days after study drug discontinuation. A hormonal contraceptive is allowed as one of the required methods of contraception, as the PK profile of hormonal contraceptives has been shown not to be substantially altered in the presence of ponesimod.

More detailed information can be found in the Investigator's Brochure [Ponesimod IB].

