1.4.8 Statistical hypotheses and sample size

No statistical hypothesis has been set for this study. The sample size will depend solely on the number of patients who complete their regular Week-24 (EOT) visit in the core study while on study treatment and who decide to participate in this extension study.

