5.4.4.2. Frequency and AEs per 100 subject-years

AEs are summarized according to both frequency (number of subjects and percentage) and AEs per 100 subject-years (number of events and rate) and based on various grouping terms (for example MedDRA preferred term, or MedDRA primary system organ class).

For frequency of subjects experiencing an AE, AEs reported more than once for a subject with the Analysis Period (based on grouping term) are counted only once per subject.

AEs per 100 subject-years is calculated as (Total cumulative number of events during the Analysis Period / Cumulative observation time over all subjects (years) during the Analysis Period) \times 100, per grouping term. Pregnancy interruptions and events during pregnancy interruptions should be excluded from this calculation.

For total cumulative number of events, multiple records of the same MedDRA preferred term in the AE dataset for the same subject count as individual events (episodes of the same type of event) unless they have the same start date.

The observation time (in days) per subject for summaries of treatment-emergent AEs is calculated as: minimum (date of last administration of ponesimod within the Analysis Period +15, EOS date) – ponesimod start date + 1. Pregnancy interruptions should be excluded from this calculation.

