6.8. Appendix 8 Adverse Events of Special Interest

Adverse events of special interest (AESIs) include the anticipated risks of treatment with ponesimod and events that may be related to MS co-morbidities.

The definitions for AESIs are based on the systematic approach using Standardized MedDRA Queries (SMQ). The additional relevant terms can be added to the search or deleted appropriately providing the rationale for the change. The proposal is based on MedDRA version 26.0. The following safety areas are addressed by the pre-defined AESIs:

The following categories for adverse events of special interest (AESI) are defined:

- Bradyarrhythmia occurring post-first dose
- Macular edema
- Bronchoconstriction
- Severe liver injury
- Serious opportunistic infections including PML
- Skin cancer
- Non-skin malignancy
- Convulsions
- Unexpected neurological or psychiatric symptoms/ signs (PRES, ADEM, atypical MS relapses)

Infection related AEs are identified by the AEs belonging to the MedDRA system organ class (SOC) "Infections and Infestations" (primary SOC), only if reported as serious or severe. If the intensity information is missing, the AE is conservatively considered to be of severe intensity.

See below for the search criteria (based on preferred terms and/or standardized MedDRA queries) used for pre-defined AEs to be included in the above safety areas of special interest.

The time to first treatment-emergent AESI in AP3 for each AESI category (in days) is defined as [date of first treatment-emergent AE in AESI category – ponesimod start date + 1] in days. If first treatment-emergent AE in AESI category is after the restart of treatment after pregnancy interruption period, then the time to first treatment-emergent AESI in AP3 (in days) is defined as: [date of first treatment-emergent AE in AESI category – ponesimod start date + 1 – (end of pregnancy interruption – (start of pregnancy interruption + 15) + 1)]

Subjects without any treatment-emergent AEs in a given AESI category during AP3 are censored, and censored time is defined as (the minimum of [last administration of ponesimod in AP3 +15 days, last study date] – ponesimod start date + 1. For subjects with pregnancy interruption: the minimum of [last administration of ponesimod in AP3 +15 days, last study date] – ponesimod start date + 1 – (end of pregnancy interruption – (start of pregnancy interruption + 15) + 1)

Statistical Aliarysis Fiall AC-030D202
--

AESI	SMQ	РТ

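### The Final CSR drops time to first AESI because the 2019 interim showed it, so no summary table shows how late-onset AESI risk behaves beyond about 8 to 9 years of exposure

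*SAP*

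**What the plan says.** SAP 5.4.4.4.5 lists two AESI summary tables for the ponesimod period from first dose to last study date (AP3). One is "Treatment-emergent AESIs by AESI category and PT (frequency"), and the other gives events per 100 subject-years by the same grouping. A listing of all AESIs is also kept. The section describes a Kaplan-Meier analysis of time to first AESI for each category, then withdraws it: "Time to first treatment-emergent AESI for each AESI category for AP3, using the Kaplan-Meier method, was presented in the Interim Analysis CSR", and the sentence goes on to say that it is not planned for the Final CSR. SAP 6.2.3 records the removal with the same reason.

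SAP 5.4.4.2 defines the rate as one pooled figure: "AEs per 100 subject-years is calculated as (Total cumulative number of events during the Analysis Period", divided by the total observation time. SAP 6.8 still carries the event time, the censoring rule and the pregnancy-interruption adjustment, beginning "The time to first treatment-emergent AESI in AP3 for each AESI category (in days) is defined as". The exposure-duration subgroup in SAP 5.5.6 (up to 4, over 4 to 8, over 8 years) is restricted to pulmonary function tests.

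Long-term safety and tolerability is the first objective in Protocol section 2 and SAP 1.1.

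**The concern.** The only reason given for dropping the analysis is that the interim report contained it. In the same section, the Days 1-21 heart-rate tables are dropped because no further data are expected. That reason is sound for those tables, since nobody new starts treatment. It is not given for the Kaplan-Meier analysis and could not be: each additional year adds follow-up at the right-hand end of the curve.

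Several AESI categories in SAP 6.8 (skin cancer, non-skin malignancy, serious opportunistic infections including PML) are ones for which risk by length of exposure is the natural long-term question. Without a time-resolved summary, the final report can say how many such events occurred but not whether they become more frequent late in treatment. Elsewhere the SAP does resolve outcomes by time: relapse rate by year (5.3.2.3), Kaplan-Meier for first relapse (5.3.2.5) and for confirmed disability accumulation (5.3.6.1), and pulmonary function by exposure duration (5.4.5.5).

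**Working it through.** **Maximum exposure.** Protocol 1.4.6 gives 24 weeks in the core study plus 96 plus 540 in the extension. 24 + 96 + 540 = 660 weeks, as stated. 660 × 7 / 365.25 = 12.65 years; the protocol prints 12.8, about 1% higher.

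**What the interim could see.** The cut-off was 31 March 2019 (Protocol 1.3.2.4). First visits in the extension ran from Q2 2010 to Q2 2011 (Protocol synopsis). Potential follow-up at the cut-off was:

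- last entrant, from first extension dose (1 April to 30 June 2011): 8.00 to 7.75 years;
- last entrant already on ponesimod in the core study (add 24 weeks): 8.46 to 8.21 years;
- first entrant, from first extension dose (1 April to 30 June 2010): 9.00 to 8.75 years; with the core study, 9.46 to 9.21 years.

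Every subject therefore had at least 7.75 years of potential follow-up, and no curve could run much past 9 years.

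**What the final data can add.** From 31 March 2019 to Q4 2023 (1 October to 31 December) is 4.50 to 4.75 calendar years. The new information lies mainly between about 8 and 12.65 years since first dose.

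**Can the retained tables show timing?** This is an illustration for one dose group, not a forecast. Assumptions: 10 first events; 817 subject-years, the interim figure for 20 mg ("corresponding to a total of 817 subject-years"), used only for scale; exponential dropout at rate λ; maximum 12.65 years. Group size N is taken as 116 to 155, because 464 randomized in four equal arms gives 116, and a third of the placebo arm (39) could join in the extension. The actual N is not given.

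- Subject-years between years a and b: PY(a,b) = N(e^(−λa) − e^(−λb))/λ. Solving PY(0, 12.65) = 817 gives λ = 0.1038 for N = 116 and 0.1667 for N = 155.
- Hazard in the window where events fall: h = 10 / PY(a,b). Cumulative incidence at the end of the window: 1 − exp(−h(b − a)).
- Pooled rate in every case: 100 × 10/817 = 1.22. Crude percentage: 10/155 to 10/116 = 6.5 to 8.6%.

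| Onset pattern | Rate per 100 subject-years | Crude % | Cum. inc. 6 months | 8 years | 12.65 years |
|---|---|---|---|---|---|
| Even | 1.22 | 6.5–8.6 | 0.6% | 9.3% | 14.3% |
| All in first 6 months | 1.22 | 6.5–8.6 | 6.5–8.5% | 6.5–8.5% | 6.5–8.5% |
| All after year 8 | 1.22 | 6.5–8.6 | 0% | 0% | 22.1–29.7% |

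For the late pattern with N = 116, h is 0.0536 per year, and 1 − exp(−0.0536 × 4.65) = 22.1%. The two retained statistics are identical in all three rows; only a time-resolved summary separates them.

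**The case against.** The strongest reply is that nothing promised has been lost. Protocol 5.6 asks for AE tabulations and listings, not a time-to-AESI analysis. The study is exploratory ("No statistical hypothesis has been set for this study"), and the removal is openly logged. Calendar years are also not subject-years: treatment stops when ponesimod becomes commercially available in the patient's country, and the documents do not say how many subjects remained after 2019. All of this stands. It limits the point to an improvement and leaves its yield uncertain.

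A reader might infer more than the documents support:

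- **That early-onset risk is hidden too.** The SAP says the interim report gave the AESI curves and the Days 1-21 tables. All subjects had at least 7.75 years of potential follow-up by then, and the Global Amendment 11 rationale says no new patients will start.
- **That the pooled rate seriously dilutes macular edema.** A dilution factor needs a group size that is not given and needs all cases to fall in the first 6 months. The amendment rationale says only that "most cases occur within the first 6 months of treatment". It also concerns the window that the interim already showed.
- **That only a percentage and a rate remain.** A subject-level AESI listing is kept, although its columns are not specified.
- **That the rate assumes a constant hazard.** It is a valid average over the period. It misleads only if read as the risk at a particular time.

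**Conclusion.** The point holds for late-onset risk in the Final CSR. AESI timing beyond about 8 to 9 years of exposure gets no time-resolved summary table, and the reason given for dropping the analysis does not cover data collected after 31 March 2019. The size cannot be fixed from the documents. The illustration shows that the retained tables would look the same whether cumulative incidence at 12.65 years were 14.3% or 22.1 to 29.7%, under an assumed event count, group size and dropout pattern.

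The interim curves are only a partial substitute even where they overlap. SAP 6.2.3 records that AESI terms and the MedDRA version were updated and that the pregnancy-interruption rule came in with a 2022 snapshot, so interim curves and final counts may not share definitions. The interim report is not among the documents, so its content is taken from the SAP. This is a cheap improvement towards the study's first objective, not a broken commitment.

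**What to change.** In SAP 5.4.4.4.5, delete the sentence stating that time to first AESI is not planned for the Final CSR, and delete the matching row in 6.2.3. Re-run the Kaplan-Meier analysis for each AESI category on final data with the 6.8 derivation. Report cumulative incidence with 95% CI and numbers at risk. Present it pooled over dose groups as well as by first randomized dose, because all subjects in treatment period 3 receive 20 mg and late curves by first dose do not reflect current dose.

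At minimum, give AESI rates per 100 subject-years in the SAP's existing bands (up to 4, over 4 to 8, over 8 years). Allocate each subject's time and events to the band in which they occur. Classifying subjects by total exposure, as SAP 5.5.6 does, would mix early and late events of long-treated subjects.

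The cost is SAP wording and a modest number of extra outputs. The analysis was programmed for the interim but must be re-run with the updated AESI terms. Late intervals will be wide and describe only subjects still under observation, which is why numbers at risk are needed.
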